NCT01731678

April 29, 2012

Transcranial Magnetic Stimulation for Adolescent Depression (TMSAD)

INTRODUCTION

Treatment options for major depressive disorder (MDD) in youth are limited, with concerns over efficacy (Carvalho et al., 2007) and safety (Adegbite-Adeniyi et al., 2012; Menke et al., 2012; Cipriani et al., 2016). Evidence suggests 30-50% of adolescents and young adults with MDD are treatment-resistant, leading to lifelong consequences (Fava, 2003). Consequently, new interventions for treatment-resistant MDD in youth are needed (Souery et al., 2011). One potential treatment is repetitive transcranial magnetic stimulation (rTMS)(MacMaster et al., 2016). Prior research demonstrates that rTMS targeting the left dorsolateral prefrontal cortex (DLPFC) in adults is well-tolerated, safe, and effective for MDD (George, 2010; Lefaucheur et al., 2014; Leggett et al., 2015; Milev et al., 2016; McClintock et al., 2017). Prior studies (case series and reports) of rTMS in MDD patients below the age of 22 are limited but encouraging, but substantial knowledge gaps remain (Donaldson et al., 2014).

OBJECTIVE

With this in mind, we conducted a trial of LDLPFC rTMS in youth with treatment resistant MDD. We hypothesized that rTMS would reduce depressive symptom severity in youth with MDD.

DESIGN

Open label trial of TMS.

METHODS

This study was approved by the Conjoint Health Research Ethics Board (CHREB) for the University of Calgary.

Participants

Participants were recruited from the community and clinics in our area. Inclusion criteria were: (1) age 12-22 years, (2) diagnosis of MDD, based on an interview with the Kiddie Schedule for Affective Disorders and Schizophrenia Present and Lifetime version (K-SADS-PL)(Kaufman et al., 1997) with a symptom severity of 40 or greater on the Children's Depression Rating Scale Revised (CDRS-R)(Poznanski et al., 1985), (3) history of failing to respond to at least one selective serotonin reuptake inhibitors (SSRI) trial (minimum 8-week treatment at an adequate dose; retrospectively determined on interview), and (4) ability to provide informed consent. Psychotropic medications were allowed if the dose has been stable for six weeks with adequate compliance, and with a commitment to not change

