medication/dosage during the trial period, unless deemed medically necessary. Exclusion criteria included: (1) previous seizures or epilepsy, (2) hypertension, (3) previous neurological or psychiatric diagnoses (specifically - bipolar disorder or psychosis) (4) pregnancy, (5) implanted metal or medical device, or (6) left-handedness.

Assessments

Participants were assessed at baseline, weekly during rTMS, and at the completion of treatment. Core clinical assessments were designed to confirm diagnosis (baseline), define symptoms, and assess treatment response. The K-SADS-PL (Kaufman et al., 1997), was used to assess both present and lifetime psychiatric symptomatology. The CDRS-R (Poznanski et al., 1985) was administered at baseline and treatment completion to quantify moderate to severe depressive symptom severity in participants. The Hamilton Depression Rating Scale (Ham-D)(Hamilton, 1967) and Beck Depression Inventory (BDI)(Beck et al., 1997), were used to assess depressive symptoms at baseline, the end of each week for safety monitoring, and after treatment completion. The Hamilton Anxiety Rating Scale (Ham-A)(Hamilton, 1959), to assess anxiety levels, was also administered at baseline and after treatment completion. We endeavored to complete assessments within two weeks of initiation and termination of rTMS.

The primary outcome measure of treatment response was defined as a greater than 50% reduction in Ham-D scores from baseline to end-point. A secondary exploratory measure of clinically meaningful response was also preset at 30% based on American College of Neuropsychopharmacology (ACNP) recommendations (Rush et al., 2006). We also examined predefined criteria for remission (Ham-D score ≤ 7 post-rTMS) and partial remission (Ham-D score ≤ 10 post-rTMS and a $\geq 50\%$ reduction in Ham-D score).

rTMS

TMS was performed at the Alberta Children's Hospital. The TMS intervention utilized a Magstim SuperRapid₂, air-cooled 90mm figure-of-8-coil (Magstim, Wales UK). Using a neuronavigation system (Brainsight2, Rogue Research, Montreal), the TMS coil was monitored in real time and co-registered with the individual's structural MRI. Imaging was performed on a 3T GE MR750w scanner using a 24-channel head coil. Anatomical scan parameters were: Axial T1-w 3D BRAVO with TR = 8204 milliseconds, TE = 3.168 milliseconds, flip angle = 10 degrees, 226 slices with 0.8 mm thickness, 300 x 300 matrix.

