On the first day, motor evoked potentials (MEP) were recorded to determine the resting motor threshold (RMT) in the standard manner (Kirton et al., 2010). To initially locate the DLPFC target site, the 5-cm rule was applied, in which the scalp position 5cm anterior to the hotspot along a line to the nasion was marked (George et al., 1995; George et al., 1996; Herwig et al., 2001; Herwig et al., 2003). Neuronavigation confirmed accurate DLPFC (adjusted if needed) targeting. The TMS coil was subsequently placed tangential to the scalp, and angled at 45 degrees to the midline and fixed over the target using a mechanical arm. The target was marked on the neuronavigation system, allowing real time targeting and accurate session to session reliability.

rTMS was applied at 10 Hz. Each train consisted of 40 suprathreshold (120% RMT) pulses over 4 seconds with an inter-train interval of 26 seconds. Treatment sessions lasted 37.5 minutes (75 trains/3000 pulses), and occurred at the same time of day on every weekday for a period of three weeks (15 days total). During TMS, only passive activities were allowed (i.e., watching movies or TV, listening to music). Three weeks of treatment was selected based on existing rTMS evidence in adult MDD and our rTMS experience in pediatric stroke (Kirton et al., 2008; Davis, 2014). Participants were monitored for adverse events and tolerability using a Pediatric TMS Safety and Tolerability Measure (Garvey, 2005) on days 1, 6, and 11. Items were self-rated.

STATISTICAL CONSIDERATIONS

For the primary outcome, we hypothesized that rTMS would result in a significant reduction in depression symptom severity as measured by the Ham-D. We used a paired t-test comparing baseline to post-rTMS with $p < 0.005$. We increased the threshold in keeping with recommendations designed to improve reproducibility (Benjamin et al., 2017). For exploratory measures (i.e., CDRS, BDI, Ham-A) we used a paired t-test comparing baseline to post-rTMS with $p < 0.01$ to correct for multiple comparisons (Bonferroni). Analyses were performed with IBM SPSS (version 24; New York, USA).

REFERENCES

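### Is the 0.01 threshold for the three exploratory tests unsound because the plan gives no family alpha or divisor for its Bonferroni correction?

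*Combined protocol and SAP*

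**What the plan says.** The STATISTICAL CONSIDERATIONS section sets two thresholds.

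- Primary: one paired t-test of baseline against post-treatment Ham-D at p < 0.005. The reason given is reproducibility: "We increased the threshold in keeping with recommendations designed to improve reproducibility".
- Exploratory: "For exploratory measures (i.e., CDRS, BDI, Ham-A) we used a paired t-test comparing baseline to post-rTMS with" p < 0.01, chosen "to correct for multiple comparisons (Bonferroni").

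The three scales are introduced by *i.e.*, so the list is complete: CDRS, BDI and Ham-A. No family alpha and no divisor are stated for them.

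The Assessments section names further outcomes derived from the Ham-D. One is a lower response cut-off: "A secondary exploratory measure of clinically meaningful response was also preset at 30" per cent. Remission and partial remission follow: "We also examined predefined criteria for remission". None of these has a test or a threshold.

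The text is retrospective. The OBJECTIVE section says "we conducted a trial of LDLPFC rTMS in youth with treatment resistant MDD", and the statistical section closes with "Analyses were performed with IBM SPSS".

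**The concern.** A Bonferroni threshold is the family alpha divided by the number of tests. Someone checking the plan would try 0.05/3 and get 0.0167. The stated 0.01 matches three tests only if the family alpha is 0.03, a level the plan never mentions. It matches 0.05 only if there are five comparisons, or four with 0.0125 rounded, and neither count is documented. The 30% response and remission outcomes add doubt about what the authors counted.

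The threshold decides which of CDRS-R, BDI and Ham-A are reported as improved. If the intended family alpha were below 0.03, then 0.01 would be too lenient; if it were 0.05, 0.01 would be stricter than needed and would cost power. Single-step Bonferroni can also be improved on by Holm's method at the same error bound, so the plan might seem to give up power for nothing.

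**Working it through.** **Inputs from the plan.** Number of exploratory tests k = 3; per-test threshold 0.01; primary threshold 0.005. The plan gives no sample size, effect size or correlation between scales, so every power figure below rests on assumed values.

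**1. Can 0.01 be reproduced?** Threshold = family alpha / k.

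| Family alpha | k = 3 |
|---|---|
| 0.005 | 0.0017 |
| 0.01 | 0.0033 |
| 0.03 | 0.0100 |
| 0.05 | 0.0167 |
| 0.10 | 0.0333 |

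At 0.05 with other counts: 0.05/4 = 0.0125 and 0.05/5 = 0.01. The figure therefore cannot be derived from stated inputs, because the family alpha is missing. With the three listed tests it corresponds to 0.03.

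**2. What error does the rule allow?**

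- Bound for the three tests: 3 × 0.01 = 0.03.
- If the three were independent: 1 − 0.99³ = 0.0297.
- Bound including the primary: 0.03 + 0.005 = 0.035.
- Positive correlation lowers the three-test figure. In simulations with all three nulls true it was about 0.029 at correlation 0.3, 0.027 at 0.6 (both n = 20) and 0.021 to 0.023 at 0.8 (n = 30 and n = 15).

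The rule is thus stricter than a 0.05 family level requires. Compared with 0.05/3, the only results that change are p-values between 0.01 and 0.0167, which the plan calls non-significant. The departure can remove a claim but cannot add one. The threshold would be too lenient only for a family alpha below 0.03, and nothing in the document assigns such a level to these measures. The 0.005 belongs to Ham-D alone and is justified by reproducibility, not multiplicity.

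**3. What would Holm change?** Holm at 0.03 compares the ordered p-values with 0.03/3 = 0.01, 0.03/2 = 0.015 and 0.03/1 = 0.03. Each step is at least 0.01, so it rejects everything the plan's rule rejects and sometimes more. Average power per measure is shown below for two-sided tests with the same standardised change d on all three scales; the Holm ranges cover correlations 0.3 to 0.8.

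| d | n | Fixed 0.01 | Holm at 0.03 |
|---|---|---|---|
| 0.3 | 20 | 9% | 10–11% |
| 0.3 | 30 | 15% | 17–19% |
| 0.5 | 20 | 30% | 35% |
| 0.5 | 30 | 50% | 57–58% |
| 0.5 | 40 | 67% | 74–76% |
| 0.8 | 20 | 75% | 82–84% |
| 0.8 | 30 | 94% | 97% |

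The gain runs from about 1 to 9 points. It has a price. When two measures truly improve (d = 0.8) and the third does not, the false rejection rate for the third rises from 1.0% to about 2.0–2.8% (n = 20 and 30, correlations 0.3 to 0.8). That stays within the 3% bound but is at least double.

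**4. Is the family defined?** The listed scales are the only outcomes given an exploratory test. Response and remission have no test, so read as written they are descriptive and do not enter the count.

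**The case for a change.** The strongest case for a change is that the plan chose to correct for multiplicity and named a method, and a named correction ought to be checkable. Calling 0.01 conservative presumes a 0.05 family level that the plan does not state. At matched error Holm uses the same three p-values, needs no further data and never rejects less. Stating the family and level would take a sentence or two.

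Part of this stands. The level and divisor are missing, and a reader cannot tell which calculation produced 0.01. A sentence saying that the cut-off bounds family error at 0.03 for three tests would be a courtesy.

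The rest does not lead to a change. The achieved error bound does not depend on what the authors had in mind: it follows from three tests at 0.01. Single-step Bonferroni is valid, and preferring Holm is a choice between sound methods, not a correction of an error. Holm would be an option only if the exploratory results were still unseen, and the past tense throughout points the other way. With results known, any loosening, by Holm or by moving to 0.0167, would invite the charge of picking the rule to suit the data. It would also run against a plan that deliberately adopted stricter thresholds.

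**Conclusion.** The observation is accurate, but no change to the plan follows. Applied as written, the rule limits the chance of any false positive among CDRS-R, BDI and Ham-A to 0.03 (0.035 with the primary). No conclusion becomes wrong because the derivation is unstated. An analyst has all that is needed to carry it out: the measures, the test and the cut-off. If exact p-values are reported, readers can apply any other threshold themselves.

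This rests on reading the three-scale list as complete, treating the response and remission outcomes as descriptive, and taking the past tense to mean that the analyses are finished. It concerns only whether 0.01 is an adequate threshold; the document does not show when that threshold was fixed. The power comparison depends on assumed sample sizes, effects and correlations, and so does not show a loss in this particular trial. The Ham-D test at 0.005 is unaffected.
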